Design & Setting: We will conduct a double-blind, randomised, parallel-group controlled superiority trial with alcohol treatment outpatients at 6 AOD treatment services in Melbourne, Victoria. Participants will be randomised to one of 2 groups with a 1:1 allocation ratio. Both participants and researchers completing the follow-up interviews will be unaware (blinded) of the condition to which they have been randomly allocated.

Participants: We aim to recruit at least 300 participants receiving outpatient interventions for alcohol use disorder at the participating services. To be eligible, participants must, at the time of the screening interview:

- Be aged 18+
- Own an Android or iOS smartphone with an Australian mobile number
- Be currently accessing outpatient treatment for alcohol problems. (There is no requirement that alcohol be the *only* substance for which they are seeking treatment, and as such participants with multiple drugs of concern are eligible as long as alcohol is one of the drugs of concern for the current episode of treatment.)
- Have an Alcohol Use Disorders Identification Test (AUDIT) score of at least 8
- Not have been in residential rehabilitation within the past 4 weeks.
- Not have been in any form of inpatient treatment (e.g. hospital or residential withdrawal treatment) within the past week.
- Not entering inpatient/residential treatment within the next month.

The target sample size was determined based on practical considerations (likely recruitment rate, time available for recruitment), as there was little prior basis to estimate likely effect size of a personalised ApBM smartphone app in an outpatient client population. Nevertheless, a calculation conducted in GPower 3.1 suggested that the primary analysis (across 4 repeated measures) would have 90% power to detect a small time x group interaction effect size (partial eta squared of .01) with a sample of 178 participants (i.e., 59% retention at follow-ups). If recruitment proceeds quickly enough, we will aim to recruit more than 300 participants, to allow for increased statistical power in case attrition is larger than expected.

Measures:

Demographic information: Participants will be asked to enter their gender, the AOD service where they were recruited from, the date they began the current episode of treatment they are receiving from that service, and drugs of concern, in an online survey hosted on Qualtrics.

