Alcohol problem severity: The Alcohol Use Disorders Identification Test (AUDIT) (Saunders, Aasland, Babor, de la Fuente, & Grant, 1993) will be used at baseline to measure the severity of alcohol use and related problems. The AUDIT consists of 10 items, each scored 0-4, and total scores are calculated based on the sum of individual item scores. The AUDIT has shown strong evidence for internal consistency, with meta-analyses suggesting it is above 0.8 (Reinert & Allen, 2007). Test-retest reliability over 1-week to 1-month intervals has ranged from .87-.95 in several general population samples, and test-retest reliability of the dichotomous categorisation using the hazardous drinking cut-off score (8 or above) is also strong (Reinert & Allen, 2007). This cut-off score has 92% sensitivity and 94% specificity for detecting hazardous or harmful alcohol use when compared to classification obtained through structured clinical interview and examination (Saunders et al., 1993). While the AUDIT usually enquires about drinking and related problems in the past year, wording of instructions and questions will be modified to ask participants to base answers on the past 3 months so that equivalent, non-overlapping periods can be assessed at both baseline and the 3-month follow-up.

The Severity of Dependence Scale (SDS) (Gossop et al., 1995) will be used to measure severity of psychological dependence on alcohol in the past month. The SDS is a 5-item scale, with each item scored 0-3, and total scores are calculated by summing individual item scores. Since the SDS was initially developed to measure dependence on heroin, cocaine, and amphetamines, wording of some items will be slightly modified to enhance its relevance to alcohol, similar to the wording used by Gossop, Marsden, and Stewart (2002) when they validated the SDS for measuring alcohol dependence. Gossop et al. (2002) reported that this version of the SDS had high internal consistency (Chronbach's $\alpha=0.86$ among substance use treatment patients who had endorsed at least one SDS item for their alcohol use) and SDS scores correlated moderately with frequency of drinking, indicating its validity.

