survey that collects information on the client's first name, mobile number, treatment site, and contains a tick box to indicate the client's verbal consent. Clinicians can also provide clients with the research team's details (study email address and contact number) if the client prefers to approach the researchers themselves. These forms are to be stored by the service, and treatment service staff will send the client's name and phone number to the research team email address.

Research staff will phone clients who have provided consent to be contacted to confirm eligibility (administering the AUDIT, checking age and phone operating system, confirming that they have no plans to enter residential/inpatient treatment in the next month, confirming absence of past-month residential rehabilitation and any past-week inpatient treatment (e.g., hospitalisation or residential withdrawal), as well as asking about number of days spent in inpatient treatment in the past month if the person underwent any inpatient treatment prior to the previous week.). After confirming eligibility, the researcher will explain the study, including requirement to complete baseline and follow-up questionnaires, duration of the study, nature of confidentiality, and payments participants can receive for completing assessments. If the researcher who conducts this recruitment phone call believes the participant is too impaired to understand the information they were presented with, they will not proceed with recruitment. If the client remains interested, they will be sent (via SMS and/or email) a link to a Qualtrics page that displays the participant information sheet (the information sheet will also be sent as a pdf attachment so participants can store and access it without re-visiting the Qualtrics page). They will also be advised to enable automatic updates on their smartphone to ensure that updates to AAT-App will not disrupt functionality.

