Participants will be required to indicate that they have read and understood the information and consent to participate. This will result in the remaining baseline questionnaires being displayed including items assessing gender, which AOD treatment service the participant is attending, type(s) of treatment being accessed, drugs of concern, date of commencement of the current episode of treatment, treatment goal (abstinence or moderation), SDS, CEQ-F, and ATOP quality of life items. They will also be required to enter their smartphone number, and are encouraged to enter additional contact details (e.g., name, email, other phone numbers, and postal address) to assist with ensuring follow-ups are completed, although this is not required.

Completing the Qualtrics survey will result in an email being automatically sent to researchers, who will access the list of access codes, select the first unused code, and send the download link and access code to the participant via SMS. The researcher will record which access code was sent to which phone number. Once participants have downloaded the app, they will be prompted to enter the access code, thus resulting in either the ApBM or minimal version of the app being installed on their phone. Participants in the active condition will view a short introductory animation explaining how the ApBM intervention works, while participants in the minimal condition will be onboarded through written text that ensures blinding is maintained (see details provided above). Participants will then be required to complete the baseline alcohol consumption questions, before completing the pre-training VAS craving measure, the AAT, and the post-training VAS craving measure. Participants in the active condition will then proceed to the image selection feature, where they will be prompted to upload or select 6 alcohol-related images and 6 positive images to be used in the ApBM training task. These participants will then complete the pre-training VAS craving measure, their first session of the ApBM task, and the post-training VAS craving measure.

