Twenty-eight days later (i.e., 56 days post-baseline), participants will be prompted with an app notification reminder to report their past-month alcohol consumption via the in-app calendar (this link will expire if it is not completed within 14 days). They will then receive an in-app link to a 1-month follow-up Qualtrics survey measuring SDS, CEQ-F and ATOP and asking about past-month residential/inpatient treatment. They will be reimbursed with a \$20 supermarket voucher for completing this follow-up within this 2-week data collection window (i.e., 56-70 days post-baseline).

Finally, 56 days later (i.e., 112 days post-baseline) participants will be prompted with another app notification reminder to report their past-month alcohol consumption via the in-app calendar (this link will expire if the survey is not completed within 28 days). They will then receive an in-app link to a 3-month follow-up Qualtrics survey measuring SDS, CEQ-F, ATOP and AUDIT scores, and asking about past-month residential/inpatient treatment. They will receive a \$20 supermarket voucher if they complete this survey within the 4-week data collection window (112-140 days post-baseline).

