first 10 interviews are completed, we will review the representativeness of the sample, in terms of gender, age and phone type (iOS or Android), and may attempt to target further recruitment more specifically (e.g., by only inviting participants of certain age groups or gender to participate) if the sample appears unrepresentative. An unblinded researcher (not involved in follow-ups) will phone participants to briefly explain the qualitative study, including the study's purpose, the approximate duration of the interview, the opportunity to receive \$40 reimbursement, that the interview is audio-recorded, and the measures taken to preserve participants' confidentiality. If participants remain interested in participating, the researcher will schedule a time to complete the interview and send the participant information sheet as an attachment by SMS or email. At the agreed interview time, the researcher will phone the participant, remind them that the interview will be recorded, and obtain audio-recorded verbal consent to participate. Once consented, the researcher will conduct the interview according to the interview schedule detailed in Appendix 1. Upon completion of the interview, participants will be reimbursed with a \$40 supermarket voucher.

Data management

Questionnaire data will be stored in Qualtrics databases, all located within a Monash University-hosted, password-protected Qualtrics account with access limited to members of the research team. These databases will include:

- Client referral data (first name, phone number, treatment site, verbal consent to provide research staff with contact details), entered into Qualtrics by clinicians who complete the client referral and verbal consent form online.
- Researcher-collected screening data (AUDIT, age, phone operating system), entered into Qualtrics by the researcher who conducts the screening questionnaire, along with the participant's phone number (used to link these data with data collected in other questionnaires).
- Baseline, post-intervention, 1-month, and 3-month follow-up questionnaire databases, with data entered by participants via the online surveys. As noted above, participants also enter their smartphone number in the baseline survey to receive an app access code, and are asked to enter their phone number at follow-ups to receive their gift card, and this will allow linking of data across separate time-points.

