Secondary outcomes: Continuous outcome variables (CEQ, SDS, AUDIT, past-week HDDs, past-month drinking days, ATOP items, and approach bias) will be analysed in a similar manner to the primary analysis described above. In analyses of CEQ, SDS, past-week HDDs, past-month drinking days, and the 3 ATOP items, there will be 4 levels of time (baseline, post-intervention, 1-month, and 3-month follow-ups). Sensitivity analysis of past-week drinking days to control for the possible effect of past-week residential/inpatient treatment will be conducted as described for the primary outcome. Past-month drinking days will be expressed as a percentage of the total number of days on which a participant had the opportunity to drink (i.e., if a participant was in residential/inpatient treatment for 10 days at a certain time point, then for that time point, their past-month drinking days will be expressed as a proportion of the remaining 18 days on which they had the opportunity to drink), although data will be excluded at any time point where the participant did not have at least 14 days on which they had the opportunity to drink alcohol (i.e., if they were within residential/inpatient treatment on 15 or more days). For CEQ, secondary analyses will be conducted for each of its 3 subscales. Analyses of AUDIT scores will use 2 levels of time (baseline, 3-month follow-up). Approach bias analyses will also use 2 levels of time (baseline, post-intervention) and approach bias scores will be analysed separately for alcohol and positive images. As past-month HDDs can only be calculated at 1 time point (post-intervention), they will simply be compared between groups using a t-test post-intervention after converting scores to a proportion of days on which the participant had an opportunity to drink (as described for past-month drinking days). Proportions of groups reporting complete past-week and past-month abstinence will be compared between groups at post-intervention, 1-month follow-up, and 3-month follow-up using Pearson's chi-squared. uMARS "functionality", "aesthetics", and "subjective quality" scores, and participants' subjective ratings regarding AAT-App's effect on drinking and cravings will be explored within each group separately using descriptive data (e.g., mean, median, quartile cut-offs, percentages scoring above 3) to quantify typical ratings and proportions of participants providing favourable ratings. Where relevant, exploratory analyses will also compare mean scores of uMARS scales between groups using t-tests.

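### AUDIT is asked by a researcher at baseline and self-completed online at 3 months: the between-arm test stands, but the time effect and within-arm declines cannot be read as real change

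*Combined protocol and SAP*

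**What the plan says.** **Baseline.** The eligibility list under Participants requires that a person "Have an Alcohol Use Disorders Identification Test (AUDIT) score of at least 8". Under Procedure, research staff obtain this by phone, "administering the AUDIT, checking age and phone operating system" among other checks. Data management confirms who records it: "Researcher-collected screening data (AUDIT, age, phone operating system), entered into Qualtrics by the researcher who conducts the screening questionnaire". On the same call, "After confirming eligibility, the researcher will explain the study, including requirement to complete baseline and follow-up questionnaires, duration of the study, nature of confidentiality", so the AUDIT comes before that explanation. The online baseline survey, completed after consent and before the access code is sent, ends its list with "treatment goal (abstinence or moderation), SDS, CEQ-F, and ATOP quality of life items" and does not repeat the AUDIT.

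**Follow-up.** At 3 months participants receive a "3-month follow-up Qualtrics survey measuring SDS, CEQ-F, ATOP and AUDIT scores". Data management states that participants themselves enter the follow-up questionnaires. The score has no entry threshold at this point.

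**Intent.** Under Measures, the AUDIT recall period is cut to 3 months "so that equivalent, non-overlapping periods can be assessed at both baseline and the 3-month follow-up".

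**Analysis.** Under Secondary outcomes, AUDIT is handled like the primary outcome: "Analyses of AUDIT scores will use 2 levels of time (baseline, 3-month follow-up". The primary model tests main effects of time and group and their interaction, and names the interaction as the decisive one for efficacy. Hypothesis 4 predicts a larger AUDIT decline in the ApBM arm than in the minimal arm.

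**The concern.** The plan matches the recall window at the two time points but not the way the score is obtained. At baseline a researcher asks the questions, before confidentiality has been explained, and the answer decides entry. At 3 months the participant answers alone in an online form and nothing depends on the score. SDS, CEQ-F and the ATOP items are self-completed online throughout, and drinking is reported in the app throughout, so AUDIT is the only scale outcome that changes mode.

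Two things are at stake. First, the model yields a time effect and within-arm declines that are easily reported as improvement in problem severity, and the planned data cannot separate such improvement from a change of mode. Second, if people differ in how they respond to the mode, the screening score predicts the 3-month score less well, and a contrast of changes loses precision.

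**Working it through.** **The plan's own figure.** The only sample-size figure is 178 participants (59% of 300) for 90% power on the primary interaction, with four measures and partial eta squared .01. Taking f² = .01/.99, λ = f² × 178 × 4/(1 − ρ), and 3 and 528 degrees of freedom, power is 0.902 at ρ = .5 (ρ is not stated in the plan). The figure reproduces, and 178/300 = 59.3%. It concerns weekly drinks; none is given for AUDIT. Below, 178 is used as 89 per arm. The AUDIT means, SDs, correlations, mode shifts and effects are assumptions.

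**1. Between-arm contrast.** With two time points and complete pairs, the group-by-time test is a comparison of change scores. The entry threshold acts before allocation and both arms have the same two modes, so a common shift cancels. In a simulation of 8,000 trials per scenario (88 per arm, SD 7, reliability .8, mean 14 or 22, true change −4, mode shift −2 to +4, person-level mode noise SD 0 or 3), the null difference between arms averaged −0.02 to +0.02 points and type I error was 0.046 to 0.058. With a true 2.5-point effect the estimate was 2.4 to 2.5 points in most scenarios. The lowest was 2.24, where scores met the floor of the scale.

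**2. Within-arm change.** In the same simulation at mean 22, the control arm's true change of −4 appeared as about −2.1 (shift +2), −0.1 (shift +4) or −6.0 (shift −2). The shift enters in full.

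**3. Time effect.** The SD of change is 8 × √(2(1 − ρ)), which is 8.0 at ρ = .5 and 6.2 at ρ = .7. The noncentrality is shift/SD × √178. For a 1-point shift this is 1.67 or 2.15. The probability that a two-sided .05 test is significant in the direction of the shift, with no real change, is:

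| Mode shift | ρ = .5 | ρ = .7 |
|---|---|---|
| 0.5 | 13% | 19% |
| 1 | 38% | 57% |
| 2 | 91% | 99% |

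**4. Regression to the mean from the entry threshold.** The formula is SD × φ(z)/(1 − Φ(z)) × (1 − r), with z = (8 − mean)/SD. Retest reliability r = .87 to .95 is quoted under Measures, from general population samples.
- Mean 15, SD 8: z = −0.875 and the ratio is 0.336, so 8 × 0.336 × 0.13 = 0.35, or 0.13 at r = .95.
- Mean 20, SD 8: 0.14 or 0.06.
- Mean 25, SD 7: z = −2.43 and the ratio is 0.021, so 0.02 or 0.01.

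With the lower reliability of .8 and mean 14 in the simulation, a true −4 appeared as −4.4. The effect is small throughout.

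**5. Precision of the two analyses.** In units of the outcome variance, the change contrast has variance factor 2(1 − ρ) and the baseline-adjusted comparison has 1 − ρ². The noncentrality is 0.4 × √(89/2)/√factor = 2.668/√factor, with 176 and 175 degrees of freedom.

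| ρ | Change: factor, power | Adjusted: factor, power |
|---|---|---|
| .4 | 1.20, 68% | 0.84, 83% |
| .5 | 1.00, 76% | 0.75, 87% |
| .6 | 0.80, 84% | 0.64, 91% |

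If mixing modes lowered ρ from .6 to .5, the variance of change would rise by 25% (1.00/0.80) and power would fall from 84% to 76%. Adjustment at ρ = .5 gives 87%, more than the change contrast achieves at .6. In the simulation, mode noise of SD 3 took power for a 2.5-point effect from about 0.96 to between 0.84 and 0.87.

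**The case against.** A reader might infer that the efficacy test of hypothesis 4 is itself biased by mode and selection. The documents do not support that. The hypothesis is between arms, both arms pass through the same screening call and the same online survey, and the access code is sent only after both baseline steps. Bias would need the response to mode to differ by arm, and nothing in the documents shows this.

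Nor does the plan break a promise about scores: the Measures text aims at equivalent recall periods and is silent on mode. The order of questions on the call is documented, but no figure shows that it moves answers in either direction. The online survey is not anonymous, since a phone number links responses. A uniform shift does not lower the correlation, so the loss of precision needs a further assumption that mode response varies between people.

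It can also be said that no hypothesis rests on the time effect. Everyone is in outpatient treatment with unrestricted other care, so a decline over time could not be credited to the app even with identical modes. All of this stands, and it limits the point. It does not remove it: the time effect is still a planned test, nothing warns against reading it as change, and a more precise between-arm analysis is available from scores already collected.

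One phrase in Design & Setting mentions follow-up interviews by researchers. Procedure and Data management, however, describe participant-entered surveys with researcher reminders only.

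**Conclusion.** The point holds in a limited form. The between-arm comparison of AUDIT is valid. The AUDIT time effect and within-arm declines are not interpretable as change in severity, because they carry any mode shift point for point plus roughly 0.01 to 0.35 points of regression to the mean under assumed means of 15 to 25 and SDs of 7 to 8. The size and direction of a mode shift are unknown, and zero is possible. The selection component is negligible on a 0 to 40 scale; mode is the part that could matter.

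At the same correlation, the change contrast needs more participants than a comparison adjusted for the screening score: the adjusted variance is (1 + ρ)/2 of it, or 70%, 75% and 80% at ρ = .4, .5 and .6. That gain does not depend on any mode effect. AUDIT is a secondary outcome with one follow-up, and the primary endpoint is untouched.

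**What to change.** **For all participants.** In Data Analysis, Secondary outcomes, replace the two-level time model for AUDIT with a comparison of 3-month AUDIT between arms, adjusted for the screening AUDIT score. State that the AUDIT time effect and within-arm declines will not be reported as change in problem severity, and say why. This costs a few sentences and no data collection.

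**Optional, if recruitment is still open.** Add the same 3-month-wording AUDIT to the baseline online survey, which falls after consent and before the access code. Use it only to describe within-arm change in those who completed it. Keep the screening score for eligibility and as the single covariate for everyone, so that the outcome does not acquire two baseline definitions partway through. The cost is ten extra items, a few minutes of repeated questions, and some recall of answers given on the call.
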